# 1 Background

Pelvic organ prolapse (POP) is a functional disease that has a significant impact on quality of life (1). The prevalence of pelvic organ prolapse stage 2 or higher, according to the Pelvic Organ Prolapse Quantification system (POP-Q), ranges from 37 to 50% (2,3). Treatment methods can be conservative or surgical. Conservative treatments are for patients with moderate prolapse, while treatment of symptomatic prolapse remains essentially surgical (4). Surgical techniques can be performed by abdominal or vaginal approach depending on medical history and physical exam. Laparoscopic sacrocolpopexy is often the method of choice and is successful in 80% to 100% of cases (5–8). However, this technique is not always appropriate, especially for patients who have a high anaesthesia risk and/or a multi-operated abdomen. In these cases, a vaginal approach offers an interesting surgical alternative.

Transvaginal mesh was developed to maintain the advantage of a vaginal procedure, while reducing the risk of recurrent prolapse compared with native tissue repair. Four percent of women require repeated surgery due to prolapse recurrence after surgery without mesh, and from 1% to 7% after surgery with mesh.

The US Food and Drug Administration (FDA) published two safety alerts (in 2008, then in 2011)(9) concerning the risks of transvaginal placement of surgical mesh to treat pelvic organ prolapse and urinary incontinence. However, most studies have evaluated mesh types that are no longer available on the market. They have been replaced by new lighter mesh which lack evidence of safety (10).

Restorelle® Direct Fix™ is a single incision mesh indicated for transvaginal anterior and posterior surgical repair as reinforcement of pelvic floor defects. It is an Ultra lightweight (19 g/m^2) pre-cut macroporous mesh with four lateral arms. It allows an anterior sacrospinous ligament (SSL) approach, using a disposable device (Digitex®) (**Erreur ! Source du renvoi introuvable.**) intended to deliver a suture to the operative site without direct visualization. The proximal arms of the mesh are sutured to the SSL and the distal arms of the mesh are sutured in the arcus tendinous fascia pelvis with the same device.

# 2 Participants

All adult women who had vaginal repair of pelvic organ prolapse (recurrent or not) planned with anterior Restorelle® Direct Fix™ mesh (with or without posterior mesh) were eligible. Patients are excluded if they did not attend their follow up visit within 30 days of surgery.

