# 3 Study design and settings

This is a retrospective multicenter study in gynaecology.

Data collection from patients taken care between January 2013 and December 2016, in 10 secondary and tertiary French care centers.

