## 4 Data

Preoperative assessment consists of

- a detailed medical history,
- a urogynecological examination,
- and prolapse quantification by the simplified Pelvic Organ Prolapse Quantification (POP-Q) system (measurement of total vaginal length at rest and points Ba, C/D, and Bp at maximum Valsalva) (11,12).

Anaesthesia type and concomitant surgery are reported.

Perioperative complications are graded using the Clavien-Dindo classification (13) and their management and outcome are described.

Perioperative, early (< 30 days post-operative) and late (> 30 days post-surgery) postoperative symptoms and complications are recorded.

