## 5 Information for data collection

All information required by the protocol must be recorded on the case report forms and an explanation must be provided for each missing data. The data must be collected as it is obtained and transcribed in these case report forms clearly and legibly.

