## 6 Statistical analysis

The primary outcome measure is the perioperative morbidity (up to 30 days after surgery). It comprised the number of patients with bladder wound, ureteral wound, rectum wound, abnormal bleeding requiring blood transfusion, urinary retention, urinary tract infection, hematoma, ureteral complication, second surgery, or fail of procedure.

The secondary outcome is the number of patients with late complications (up to 3 years after surgery). It includes self-catheterization, recurrent urinary tract infections, de novo urinary stress incontinence, chronic pain, vaginal mesh exposure, prolapse recurrence, de novo dyspareunia, secondary surgery, vaginal granuloma, anatomic (Ba point  $\leq -1$ ) and functional failure.

A descriptive analysis of the data will be reported. Median, range, numbers, percentages and confidence intervals were used to describe quantitative and qualitative variables, respectively. Association between demographic and clinical factors (age, body mass index, history of hysterectomy, of POP and stress urinary incontinence surgery, cystocele  $\geq 3$ , concomitant hysterectomy and concomitant sub urethral sling) and perioperative complications will be studied. Bivariate ORs and 95 % confidence intervals will be estimated. Outcomes after surgery with Restorelle® anterior alone or with sling will be compared using a chi-square or a Fisher test.

An alpha level of 0.05 will be used.

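### The primary rate runs to day 30, but any visit within 30 days qualifies a woman, and no rule covers event-free women last seen earlier

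*Combined protocol and SAP*

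**What the plan says.** Section 2 (Participants) makes one follow-up condition: "Patients are excluded if they did not attend their follow up visit within 30 days of surgery". It names no earliest day, target day or visit window.

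Section 6 (Statistical analysis) sets the outcome period: "The primary outcome measure is the perioperative morbidity (up to 30 days after surgery". The outcome is a yes/no count per woman: "It comprised the number of patients with bladder wound, ureteral wound, rectum wound" and further listed events. The summary is equally plain: "Median, range, numbers, percentages and confidence intervals were used to describe quantitative and qualitative variables". There is no person-time, censoring or missing-outcome rule.

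Three other statements bear on the point:

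- Section 3: "This is a retrospective multicenter study in gynaecology". Visits therefore fell wherever routine care at ten centres put them.
- Sections 4 and 6 look beyond day 30: "Perioperative, early (< 30 days post-operative) and late (> 30 days post-surgery) postoperative symptoms and complications are recorded", and "The secondary outcome is the number of patients with late complications (up to 3 years after surgery". No later visit is a condition of inclusion.
- Section 5 requires that "an explanation must be provided for each missing data". This is an instruction for the case report form and does not say how the analysis treats the gap.

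**The concern.** The point concerns women who are kept in the study, not those excluded for non-attendance. The qualifying visit has to fall on or before the last day of the period it is meant to cover. Read literally, a woman seen on day 7 and never again is included, although nobody observed days 8 to 30. A woman first seen on day 35, whose whole period could be reviewed, is not. The entry rule therefore does not secure observation of the primary outcome.

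In a count of women with events divided by women included, someone with no recorded event is in the denominator and not the numerator. Nothing in the plan treats her otherwise when her record stops early. Events missed in this way can only lower the crude percentage.

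Section 1 motivates the study by the lack of safety evidence for newer, lighter meshes, so an understated rate would favour the device on the question asked. The planned confidence interval reflects sampling error only. The planned odds ratios for perioperative complications use the same outcome.

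**Working it through.** **No figure of the plan to reproduce.** Section 7 takes its minimum of 100 women from a cited standard. The documents give no expected rate, visit days or event times, so what follows is an illustration on assumed inputs.

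**Which components are exposed.** Bladder, ureteral and rectal injuries and failed procedures arise in theatre and cannot be missed this way. The exposed components are mainly hematoma, urinary tract infection, retention, reoperation and ureteral complications.

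**Formula.** Observed rate = R × [s + (1 − s) × ((1 − q) + q × F(d))], so loss = R × (1 − s) × q × (1 − F(d)).

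- R: true 30-day rate, assumed 20%.
- s: share of events in theatre or before discharge, all seen; assumed 0.3 or 0.6.
- q: share of women last seen on day d, with no later record.
- F(d): share of the remaining events that have occurred by day d. Even timing: d/30, giving 0.233, 0.467 and 0.700 at days 7, 14 and 21. Front-loaded timing (exponential, mean 7 days, truncated at day 30): (1 − e^(−d/7)) / (1 − e^(−30/7)), giving 0.641, 0.877 and 0.963.

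**Loss in percentage points from 20%**

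| Last seen | s = 0.3, even timing | s = 0.6, front-loaded timing |
|---|---|---|
| 25% on day 14 | 20 × 0.7 × 0.25 × 0.533 = 1.9 | 20 × 0.4 × 0.25 × 0.123 = 0.2 |
| 25% on day 7 | 20 × 0.7 × 0.25 × 0.767 = 2.7 | 20 × 0.4 × 0.25 × 0.359 = 0.7 |
| All on day 21 | 20 × 0.7 × 0.300 = 4.2 | 20 × 0.4 × 0.037 = 0.3 |
| All on day 14 | 20 × 0.7 × 0.533 = 7.5 | 20 × 0.4 × 0.123 = 1.0 |
| All on day 7 | 20 × 0.7 × 0.767 = 10.7 | 20 × 0.4 × 0.359 = 2.9 |

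If q = 0, because every woman has a later documented contact, the loss is zero. As d approaches 30, F(d) approaches 1 and the loss vanishes.

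**What a loss of 8 points needs.** In the left-hand column at day 7, 10.7 × q = 8 gives q = 0.75. So even with the least favourable timing, about three-quarters of women must be last seen around day 7. A second set of assumptions (half of first events after discharge, spread evenly over days 3 to 30, every woman last seen on day 7) gives 23/27 × 10 = 8.5 points.

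**Scale.** An observed 20 of 100 has an exact 95% interval of 12.7% to 29.2%.

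**Check on the obvious correction.** Kaplan-Meier can err the other way. Assume 100 women and 15 events by day 15. Of the 85 event-free women, 40 stay well and never return, and 5 of the other 45 have an event later. The true and crude rates are both 20/100 = 20%. Kaplan-Meier gives 1 − 0.85 × 40/45 = 24.4%. The rate among women with an event or a contact at or after day 30 is 20/60 = 33.3%.

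**The case against.** The strongest case against the point has five parts.

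- **The bias is conditional.** The study collects complications over three years, and those records may reveal events between the early visit and day 30. This stands: the rate may be too low, but nothing shows that it is. It does not dispose of the point, because no later contact is required or checked.
- **The plan never says that unobserved days count as event-free, and it asks for missing data to be explained.** Both statements are true. The scoring is the default result of a simple count with no other rule, and an explanation on a form does not change the count.
- **The visit may have been meant as the usual one near day 30.** That is possible, and the problem would then almost vanish. The text does not say so and plans no display of visit timing that would show it.
- **Large losses are close to worst case.** This stands. They need mostly late events, evenly spread, and most or all women lost early. With front-loaded timing and a quarter last seen early, the loss is 0.2 to 0.7 points, small beside the sampling interval.
- **Kaplan-Meier assumes that women who stop attending have the same risk as those who continue.** In retrospective charts, well women may be the ones who do not return. This stands, so Kaplan-Meier should not replace the crude rate.

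A reader might also infer that centres with early visits will be shown as safer. Ascertainment could differ by centre, but section 6 plans no comparison between centres.

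**Conclusion.** The point holds as a gap in ascertainment and reporting. Sections 2 and 6 together allow a woman to enter the 30-day rate without having been observed to day 30, and the plan neither identifies such women nor says how they are analysed. The crude percentage may be biased downward for components that can arise after discharge.

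The size is unknown. On an assumed true rate of 20%, it runs from zero, through about 0.2 to 2.7 points when a quarter of women were last seen on day 14 or day 7, to 8 points or more only when most or all were last seen around day 7 and never again. These figures rest on assumed event timing and visit days, none of which the documents give.

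A reader might infer that the reported rate is known to be several points too low. The documents do not support that: they show neither early visits nor absent later contact. No comparator device or performance threshold is tested, so no pass/fail decision turns on the shift. What is affected is how far the percentage can be read as a full 30-day morbidity rate.

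**What to change.** 1. Record the date of each primary-outcome event and the date of the last documented contact (visit, call, readmission or later consultation), using the follow-up already collected.
2. Report how many women without an event were last seen before day 30, and the distribution of last-contact day.
3. Keep the crude percentage, labelled a minimum estimate because events after the last contact are not captured.
4. Beside it, give two sensitivity estimates: the rate among women with an event by day 30 or a documented contact at or after day 30, and a Kaplan-Meier estimate at day 30.
5. State that censoring may be informative because well women may not return, so both estimates may be too high and should be read with the crude rate as a range. The first tends to be the higher of the two, because it keeps every early event but drops event-free women who left early.

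The cost is two dates per woman from charts already under review and a little more analysis. The reported range may be wider or less favourable. No new patients or visits are needed. If nearly all women prove to have a contact at or after day 30, the estimates will agree and the primary result is strengthened.

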# 3 Study design and settings

This is a retrospective multicenter study in gynaecology.

Data collection from patients taken care between January 2013 and December 2016, in 10 secondary and tertiary French care centers.

## 4 Data

Preoperative assessment consists of

- a detailed medical history,
- a urogynecological examination,
- and prolapse quantification by the simplified Pelvic Organ Prolapse Quantification (POP-Q) system (measurement of total vaginal length at rest and points Ba, C/D, and Bp at maximum Valsalva) (11,12).

Anaesthesia type and concomitant surgery are reported.

Perioperative complications are graded using the Clavien-Dindo classification (13) and their management and outcome are described.

Perioperative, early (< 30 days post-operative) and late (> 30 days post-surgery) postoperative symptoms and complications are recorded.

## 5 Information for data collection

All information required by the protocol must be recorded on the case report forms and an explanation must be provided for each missing data. The data must be collected as it is obtained and transcribed in these case report forms clearly and legibly.

## 6 Statistical analysis

The primary outcome measure is the perioperative morbidity (up to 30 days after surgery). It comprised the number of patients with bladder wound, ureteral wound, rectum wound, abnormal bleeding requiring blood transfusion, urinary retention, urinary tract infection, hematoma, ureteral complication, second surgery, or fail of procedure.

The secondary outcome is the number of patients with late complications (up to 3 years after surgery). It includes self-catheterization, recurrent urinary tract infections, de novo urinary stress incontinence, chronic pain, vaginal mesh exposure, prolapse recurrence, de novo dyspareunia, secondary surgery, vaginal granuloma, anatomic (Ba point  $\leq -1$ ) and functional failure.

A descriptive analysis of the data will be reported. Median, range, numbers, percentages and confidence intervals were used to describe quantitative and qualitative variables, respectively. Association between demographic and clinical factors (age, body mass index, history of hysterectomy, of POP and stress urinary incontinence surgery, cystocele  $\geq 3$ , concomitant hysterectomy and concomitant sub urethral sling) and perioperative complications will be studied. Bivariate ORs and 95 % confidence intervals will be estimated. Outcomes after surgery with Restorelle® anterior alone or with sling will be compared using a chi-square or a Fisher test.

An alpha level of 0.05 will be used.

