## 7 Number of subjects

The largest users of Restorelle Direct Fix have been selected from all the centers specialized in the management of genital prolapse in France. This series will collect data from the first French installers. This is to obtain a representative sample of at least 100 patients, in accordance with AFNOR NF S94-801 standard (4).

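### Late complications up to 3 years are reported as crude percentages with no late denominator, follow-up cut-off or allowance for incomplete follow-up

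*Combined protocol and SAP*

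**What the plan says.** Section 6 (Statistical analysis) defines the late outcome: "The secondary outcome is the number of patients with late complications (up to 3 years after surgery". Its components mix datable events, such as mesh exposure and secondary surgery, with conditions noted at a visit, such as chronic pain, dyspareunia, the Ba point and functional failure. The summary method is general: "Median, range, numbers, percentages and confidence intervals were used to describe quantitative and qualitative variables". The same section says that outcomes with anterior mesh alone or with a sling "will be compared using a chi-square or a Fisher test", without saying which outcomes.

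The other sections that bear on follow-up are these:

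- Section 2 (Participants) has the only follow-up condition: "Patients are excluded if they did not attend their follow up visit within 30 days of surgery".
- Section 3 (Study design and settings) gives dates: "Data collection from patients taken care between January 2013 and December 2016". They are tied to when the women were cared for. They are not said to be surgery dates or the end of late follow-up.
- Section 4 (Data) says that late "postoperative symptoms and complications are recorded", where late means more than 30 days after surgery. It gives no visit schedule.
- Section 5 (Information for data collection) requires: "All information required by the protocol must be recorded on the case report forms and an explanation must be provided for each missing data". This documents gaps but does not say how a woman without late data enters a percentage.
- Section 7 (Number of subjects) sets the size: "This is to obtain a representative sample of at least 100 patients".

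**The concern.** The 30-day visit fixes a population for the primary outcome but not for the following three years. In a retrospective series, some women will be seen for years and others perhaps only once. A percentage of all included women then counts those no longer seen as free of complications. A percentage of returning women depends on who comes back. The plan does not say which is meant, and the confidence interval allows for sampling error only.

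This matters because Section 1 presents the newer, lighter meshes as short of safety evidence, and mesh exposure and prolapse recurrence are listed only in the late outcome. Without a denominator and a length of follow-up, a reader cannot tell what the late percentages estimate.

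**Working it through.** There is no plan figure to reproduce. The minimum of 100 women rests on a standard, with no expected late rate, precision target or loss allowance. Everything below is illustration: T is an assumed true 3-year risk, the hazard is constant, and λ = −ln(1−T)/3 per year (0.0744 for T = 20%, 0.0351 for T = 10%).

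**1. Cut-off alone.** Assume no loss and surgery spread evenly over the 48 months of 2013–2016. The expected crude percentage is the mean of 1 − exp(−λ·min(3, cut-off − surgery date)).

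| Assumed cut-off (end of) | Share who can reach 3 years | Reads as, T = 20% | Reads as, T = 10% |
|---|---|---|---|
| 2016 | 25% | 12.8% | 6.3% |
| 2017 | 50% | 16.9% | 8.4% |
| 2018 | 75% | 19.2% | 9.6% |
| 2019 | 100% | 20.0% | 10.0% |

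The denominator matters as much. With the 2016 cut-off and T = 10%, counting only women with an event or a full 3 years gives 0.0632/(0.0632 + 0.25 × 0.90) = 21.9%, against 6.3% of all women.

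**2. Loss with partial return.** Assume that the last routine visit is uniform over 1–36 months and that a share q of problems after it still reaches the centre. With q = 0, p0 = 1 − (e^(−λ/12) − e^(−3λ))/(λ·35/12). For T = 20% this is 1 − (0.99382 − 0.80)/0.21694 = 10.7%. For other q, p = p0 + q(T − p0). Coverage is the chance that the exact 95% interval from 100 women contains T.

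| q | Crude, T = 20% | Coverage, T = 20% | Coverage, T = 10% |
|---|---|---|---|
| 0 | 10.7% | 38% | 61% |
| 40% | 14.4% | 79% | 85% |
| 80% | 18.1% | 96% | 95% |

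The shortfall is large if few problems come back and negligible for coverage if most do.

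**3. Returning women only.** If a share a of women with and b without a complication return, the percentage is Ta/(Ta + (1−T)b). For T = 20%:

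- a = 0.90, b = 0.60: 0.18/(0.18 + 0.48) = 27.3%
- a = b = 0.75: 0.15/(0.15 + 0.60) = 20.0%
- a = 0.60, b = 0.90: 0.12/(0.12 + 0.72) = 14.3%

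**4. Is a censored estimate better?** Keep the model of step 2 with 100 women and look at 2 years. The true 2-year risk is 1 − e^(−2λ): 13.8% for T = 20% and 6.8% for T = 10%. A Kaplan-Meier estimate censored at the last routine visit is centred on the true value for every q. The crude percentage at q = 0 is c0 = 1 − [(e^(−λ/12) − e^(−2λ))/(λ·35/12) + (12/35)e^(−2λ)]. For T = 20% this is 1 − (0.6087 + 0.2955) = 9.58%. For other q, c = c0 + q(true − c0). Its total error is √(bias² + c(1−c)/100). For T = 20%, q = 0, in percentage points: √(4.24² + 2.94²) = 5.2; for q = 80%: √(0.85² + 3.36²) = 3.5.

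| T | Total error, censored (10,000 simulated studies) | Total error, crude, q = 0 / 40 / 80% |
|---|---|---|
| 20% | 4.4 points | 5.2 / 4.1 / 3.5 points |
| 10% | 3.2 points | 3.0 / 2.6 / 2.5 points |
| 5% | 2.3 points | about 1.8 points throughout |

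The censored figure removes the bias but pays in precision. It has the smaller total error only at T = 20% with no return. At T = 5% about 10% of simulated studies have no event by 2 years, so its log-log interval is undefined there. Censoring at last contact of any kind is not a substitute: for T = 20% it gives 13.8, 16.4 and 18.7% at q = 0, 40 and 80%, because women who return with a problem extend their own follow-up.

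**5. Sling comparison, only if it covers late outcomes.** Assume equal true risks of 10% or 20%, 100 women split 50/50, 80/20 or 20/80, and follow-up uniform over 0–3 v 0–1.5 years, or complete v uniform over 0–3. At alpha 0.05 the false-positive rate is 1–28% by chi-square, 0.3–20% by Fisher and 3–6% by log-rank. With complete follow-up in both groups it is 4–5% by chi-square and 2–3% by Fisher.

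**The case against.** The plan promises a description. The outcome is a number of patients, and 3 years can be read as an observation window. Counts of observed events remain valid, and nowhere are the percentages called 3-year risks. The coverage figures therefore test the interval against a target that the plan did not set. All of this stands: the defect is an undefined quantity, not a false statement. A description still needs its denominator and length of follow-up.

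The case report form is not in the documents and may already hold event and visit dates. The planned median and range could cover follow-up length, although it is not named. Both points make the fix cheaper but do not supply the missing rule.

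Most components are conditions noted at visits, and recurrence is usually found only then. Time-to-event methods suit few of them. This stands and limits the fix.

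Three stronger readings are tempting:

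- A reader might infer that December 2016 closes follow-up, so that only a quarter of women could reach 3 years. Section 3 ties the dates to care, and the quarter also assumes even accrual.
- A reader might infer that a censored estimate should replace the crude percentage. Step 4 does not support that at true risks of about 10% or less, and the documents give no expected rates.
- A reader might infer that the sling test is inflated. Section 6 does not say that it covers late outcomes, nothing suggests that follow-up differs by sling, and in some assumed settings the error rate is about 1%.

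**Conclusion.** The point holds. Section 6 gives late complications as crude percentages with confidence intervals. No section states a late denominator, an end to late follow-up or how incomplete follow-up is handled. Unless late capture is complete, a percentage of all included women understates the late risk on average, and a percentage of returning women may be too high or too low.

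The size cannot be derived from the documents. In the illustrations a true 20% reads as anything from 10.7% to 20.0% of all women, and from 14.3% to 27.3% of returning women. These figures rest on a constant hazard and on assumed accrual, loss and return. They show what the plan leaves open and do not forecast this study's error. The omission itself is certain; the harm may be large or negligible. The 30-day primary outcome is unaffected. The gap should be fixed before the late safety results are interpreted.

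**What to change.** In Section 6:

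1. State the data cut-off. Give each late percentage with its denominator, the median follow-up and the numbers still followed at 1, 2 and 3 years. This is the essential part.
2. For reasonably datable events (mesh exposure, secondary surgery), add a cumulative risk with 95% CI, censored at the last routine visit, beside the crude percentage. Name neither as the main estimate. Say that the censored figure assumes that the length of routine follow-up is unrelated to risk.
3. Report status items (Ba point, pain, dyspareunia, functional failure) among women assessed in stated visit windows.
4. Say whether the sling comparison includes late outcomes. If it does, use a method that allows for follow-up time, such as the log-rank test, for the datable events.

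The cost is SAP wording plus, where not already collected, abstraction of event and last-routine-visit dates in 10 centres. Some events may prove undatable. Intervals for the censored figures will be wider (about 18 v 12–14 points at 2 years with 100 women and T = 20%), and late rates may look less favourable.

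### Three late components (self-catheterization, recurrent urinary tract infection, chronic pain) carry no new-onset rule, so unchanged preoperative conditions can be counted as late complications

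*Combined protocol and SAP*

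**What the plan says.** The secondary outcome, in Section 6 (Statistical analysis), is the number of patients with late complications over as long as three years after surgery. Its components begin: "It includes self-catheterization, recurrent urinary tract infections, de novo urinary stress incontinence, chronic pain, vaginal mesh exposure, prolapse recurrence, de novo dyspareunia". Secondary surgery, granuloma, an anatomic criterion on point Ba and functional failure follow. The *de novo* qualifier is attached to stress incontinence and to dyspareunia only.

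The other sections bearing on onset are these:

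- Section 2 (Participants) admits "All adult women who had vaginal repair of pelvic organ prolapse (recurrent or not) planned with anterior Restorelle® Direct Fix™ mesh". Its one exclusion is about attendance: "Patients are excluded if they did not attend their follow up visit within 30 days of surgery".
- Section 4 (Data) collects "a detailed medical history" before surgery. It does not name the three conditions.
- Section 4 separates early from late events by time alone: "Perioperative, early (< 30 days post-operative) and late (> 30 days post-surgery) postoperative symptoms and complications are recorded".
- Section 6 lists among the patient factors "history of hysterectomy, of POP and stress urinary incontinence surgery", so women with earlier pelvic surgery are expected in the series.

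**The concern.** One sentence restricts two components to new onset and leaves three others unrestricted. Someone abstracting charts could reasonably take the difference in wording as a difference in rule: stress incontinence and dyspareunia must be new, while pain, infections and catheterization need only be present after day 30. All three can exist before a prolapse repair, and nothing in the eligibility criteria removes women who already have them.

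Section 1 gives the reason for the study: the newer, lighter meshes lack evidence of safety. The late count is the plan's only secondary outcome and its longer-term safety figure. It counts patients, so one carried-over condition is enough to turn a woman without any new event into a case. There is no group treated without this mesh against which such a background could be judged. The data come from charts at 10 centers, so an unstated rule may also be applied differently from one center to the next.

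**Working it through.** The plan states no late-event rate, so there is no figure to reproduce. The check has two parts.

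**1. Is there an onset rule anywhere?**

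| Place | What it could have supplied | What it supplies |
|---|---|---|
| Section 2 | Exclusion of women with the condition at baseline | Exclusion only for a missing visit within 30 days |
| Section 4, preoperative assessment | Baseline status of each condition | A general history, with the three conditions not named |
| Section 4, recording of events | Comparison with the preoperative state | Timing only, with symptoms and complications recorded together |
| Section 6, outcome definition | A new-onset limit | A limit on two components, none on these three |

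None of these places closes the gap. The definition does not say that unchanged preoperative conditions are counted, and it does not keep them out.

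**2. What would counting them do?** Let q be the share of women with a genuine late event, and b the share with at least one of the three conditions carried over from before surgery. Both are assumptions. If every carried-over case is counted and the two are independent:

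reported rate = 1 − (1 − q)(1 − b), so the increase is b(1 − q).

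| Assumed q | b = 2% | b = 5% | b = 10% | b = 15% |
|---|---|---|---|---|
| 10% | 11.8% | 14.5% | 19.0% | 23.5% |
| 20% | 21.6% | 24.0% | 28.0% | 32.0% |
| 30% | 31.4% | 33.5% | 37.0% | 40.5% |

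The increase runs from 0.02 × 0.70 = 1.4 points to 0.15 × 0.90 = 13.5 points. If the composite were already at 80% (assumed), b = 5% to 10% would add only 0.20 × 0.05 = 1 point to 0.20 × 0.10 = 2 points.

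Independence is a further assumption. Without it, the increase is the share of women with a carried-over condition and no other counted event, which lies between max(0, b − q) and min(b, 1 − q). With q = 10% and b = 10% that is anything from 0 to 10 points; independence gives 9.

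For one component taken alone, suppose there are no new cases and 10 carried-over cases in 100 women (the minimum sample in Section 7). It would be reported as 10% (exact 95% interval 4.9% to 17.6%) instead of 0% (0% to 3.6%).

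Two things follow. Counting carried-over cases can raise the late count or leave it unchanged, but cannot lower it. The amount depends entirely on quantities the documents do not give.

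**The case against.** The strongest reply is that the outcome counts complications, and a condition that preceded surgery and did not change is not ordinarily a complication of it. A careful abstractor might leave such cases out without being told to. This stands in part: the plan leaves the matter to discretion and does not prescribe the broad reading. But the selective qualifier in the same sentence points the other way, and discretion spread over 10 centers is itself a weakness in a safety count.

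A second reply is that the analysis is descriptive and the list already mixes new harm with treatment failure. Prolapse recurrence and an undefined functional failure are both in it, so an onset rule for three components would not turn the composite into a pure new-harm rate. That is true of the composite. The three component rates would still become interpretable.

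Third, chart silence does not prove absence, and judging worsening needs a baseline severity measure, which Section 4 does not name for pain or infections. This stands and shapes the fix.

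Fourth, carry-over of similar frequency with and without a sling would not by itself create a difference in that comparison. Correct, but the groups are not randomised and similarity cannot be presumed.

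A reader might also infer that exposures or granulomas from an older implant will be attributed to this mesh. The documents mention earlier prolapse and incontinence surgery but never say that earlier implants were present. A rule limiting these events to the site of the new implant could also drop genuine device events. That inference is not supported.

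**Conclusion.** The definition is incomplete in a way that matters for a safety series and should be corrected. As written, self-catheterization, recurrent urinary tract infections and chronic pain that were present before surgery and unchanged by it can be counted as late complications, possibly differently across centers. The possible bias in these component rates and in the late count is upward.

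A reader might go further and conclude that such cases are counted, or that the late rate is inflated by a known number of points. The documents support neither. No sentence directs that they be counted, and every numerical illustration here rests on an assumed baseline prevalence, event rate and, in the table, independence. The illustrations show the mechanism and its direction and are not evidence of size.

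The reach is limited. The primary outcome, the sample size and the planned odds ratios for perioperative complications are unaffected.

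**What to change.** In Section 6, define the three components as late complications when they are new after surgery compared with the preoperative record, or documented as worse where the chart allows that judgement. In Section 4 and on the case report form, add one preoperative item for each of the three, coded yes, no or unknown and taken from the history already collected.

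Report on separate lines:

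- new or documented-worse cases;
- persisting cases that were present before surgery;
- cases with unknown baseline.

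Keep the count of all cases regardless of baseline as a sensitivity figure. The new-or-worse count and the all-cases count then bracket the result, provided the charts coded yes or no are correct.

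This extends a restriction the plan already applies to two components, uses charts already being abstracted, and needs no further patients or visits. The cost is three added items and some charts with unknown baseline status. How many cannot be told from the documents, so the unknowns should be shown and not assumed to be absent. No site rule for mesh exposure or granuloma is needed.
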